## **6.0 Expected Adverse Events/Dose Modifications**

### **Expected Adverse Events Associated with Imatinib Mesylate**

#### Chronic Myeloid Leukemia

The majority of Imatinib Mesylate-treated patients experienced adverse events at some time. Most events were of mild to moderate grade, but drug was discontinued for adverse events in 2% of patients in chronic phase, 3% in accelerated phase and 5% in blast crisis.

The most frequently reported drug-related adverse events were nausea, vomiting, diarrhea, edema, and muscle cramps (Table 3 for newly diagnosed CML, Table 1-5 for other CML patients). Edema was most frequently periorbital or in lower limbs and was managed with diuretics, other supportive measures, or by reducing the dose of Imatinib Mesylate. The frequency of severe superficial edema was 0.9%-5%.

**Table 3      Adverse Experiences Reported in Newly Diagnosed CML Clinical Trial  
(>10% of all patients)**

Preferred term 	All grades		CTC grades 3/4	
	Gleevec N=551 (%)	IFN+Ara-C N=533 (%)	Gleevec N=551 (%)	IFN+Ara-C N=533 (%)
Fluid retention	54.1	10.1	0.9	0.9
- Superficial edema	53.2	8.8	0.9	0.4
- Other fluid retention events	3.4	1.5	0	0.6
Nausea	42.5	60.8	0.4	5.1
Muscle cramps	35.4	9.9	1.1	0.2
Musculoskeletal pain	33.6	40.5	2.7	7.7
Rash	31.9	25.0	2.0	2.1
Fatigue	30.7	64.7	1.1	24.0
Diarrhea	30.3	40.9	1.3	3.2
Headache	28.5	41.8	0.4	3.2
Joint pain	26.7	38.3	2.2	6.8
Abdominal pain	23.4	22.9	2.0	3.6
Myalgia	20.9	38.6	1.5	8.1
Nasopharyngitis	19.2	7.7	0	0.2
Hemorrhage	18.9	19.9	0.7	1.3
Dyspepsia	15.1	9.0	0	0.8
Vomiting	14.7	26.6	0.9	3.4
Pharyngolaryngeal pain	14.2	11.4	0.2	0
Dizziness	13.2	23.1	0.5	3.4
Cough	12.5	21.6	0.2	0.6
Upper respiratory tract infection	12.5	7.9	0.2	0.4
Pyrexia	11.8	38.6	0.5	2.8
Weight increased	11.6	1.5	0.7	0.2
Insomnia	11.4	18.4	0	2.3

 All adverse events occurring in  $\geq 10\%$  of patients are listed regardless of suspected relationship to treatment.

**Table 4** Adverse experiences in greater than or equal to 10% of patients during phase II leukemia studies

Preferred term (% of patients)	Myeloid blast crisis n= 260		Accelerated phase n=235		Chronic phase n=532	
	All grades	Grade 3/4	All grades	Grade 3/4	All grades	Grade 3/4
Nausea	70	4	71	5	60	2
Fluid retention	71	12	73	6	66	3
Superficial edemas	67	5	71	4	64	2
Other fluid retention events	22	8	10	3	7	2
Muscle cramps	27	0.8	42	0.4	55	1
Diarrhea	42	4	55	4	43	2
Vomiting	54	4	56	3	32	1
Hemorrhage	52	19	44	9	22	2
CNS hemorrhage	7	5	2	0.9	1	1
Gastrointestinal hemorrhage	8	3	5	3	2	0.4
Musculoskeletal pain	43	9	46	9	35	2
Skin rash	35	5	44	4	42	3
Headache	27	5	30	2	34	0.2
Fatigue	29	3	41	4	40	1
Arthralgia	25	4	31	6	36	1
Dyspepsia	11	0	21	0	24	0
Myalgia	8	0	22	2	25	0.2
Weight increased	5	0.8	14	3	30	5
Pyrexia	41	7	39	8	17	1
Abdominal pain	31	6	33	3	29	0.6
Cough	14	0.8	26	0.9	17	0
Dyspnea	14	4	20	7	9	0.6
Anorexia	14	2	17	2	6	0
Constipation	15	2	15	0.9	6	0.2
Nasopharingitis	8	0	16	0	18	0.2
Night sweats	12	0.8	14	1	10	0.2
Pruritus	8	1	13	0.9	12	0.8
Epistaxis	13	3	13	0	5	0.2
Hypokalemia	13	4	8	2	5	0.2
Petechiae	10	2	5	0.9	1	0
Pneumonia	12	6	8	6	3	0.8
Weakness	12	3	9	3	7	0.2
Upper respiratory tract infection	3	0	9	0.4	15	0
Dizziness	11	0.4	12	0	13	0.2
Insomnia	10	0	13	0	13	0.2
Sore throat	8	0	11	0	11	0

With the exception of grade 1/2 edema (but not grade 3/4), there were no obvious differences in the incidence of AEs in patients treated at 400 and 600mg. However, the interpretation of a dose relationship is confounded by the fact that many patients were dose-escalated over time and in all studies AEs were analyzed according to starting dose. Patients aged  $\geq$  65 years also experienced a higher incidence of edema.

Less than 50% of patients required dose reduction at any time. Temporary treatment interruptions were required in 25-40% of patients. Despite these dose changes, the overall median dose-intensity (expressed in mg/day) in each study remained close to the initially planned dose.

#### Clinically important adverse events

Because of their relative frequency and clinical significance, several AEs occurring during the phase II leukemia trials were analyzed in greater detail, as summarized below.

##### Edema and fluid retention

Superficial edema was one of the most frequently reported AEs but was rarely severe (2-5% Grade 3/4). The most frequently involved sites included the periorbital region, face and lower limbs. The edema usually appeared within the first two months of treatment. A minority of patients with severe edema required dose reduction.

A minority (<5%) of patients developed central collections of fluid (described collectively using the term 'fluid retention') including one or more of the following: congestive heart failure, pleural effusion, ascites, pericardial effusion and pulmonary edema. It is unclear if the mechanisms underlying peripheral edema and fluid retention are the same. Fluid retention was usually managed with diuretics and/or dose reduction, or with temporary treatment interruption.

##### Gastrointestinal and CNS hemorrhages

In toxicology studies, imatinib was shown to be a local irritant and for that reason, the pattern of GI tract hemorrhages was carefully reviewed. These events were rare, and severe (Grade 3/4) cases were reported only in advanced CML patients. GI hemorrhages occurred in 3-5% of patients with advanced CML, were considered drug-related in 0-2% and severe in <1.5%. Contributing factors such as severe thrombopenia, the use of concomitant NSAIDS and a history of gastric ulcer were present in most but not all cases. Upper GI ulceration (esophageal, gastric or duodenal) or gastritis/duodenitis were visualized at gastroscopy in approximately 50% of patients with GI bleeding. Less than 1% of patients discontinued therapy as a result of these events.

Cerebral hemorrhages (including subdural hematomas and hygromas) were also reported almost exclusively in advanced CML patients (1-7%). The majority occurred in the context of rapidly progressive disease, with concomitant thrombocytopenia..

##### Skin rash

An erythematous, pruritic, maculopapular skin rash, most prominent over the forearms and trunk but occasionally present also on the face, was reported in up to 44% of patients treated with imatinib. Onset was generally within the first month of therapy. Eosinophilia was rarely seen and skin biopsies showed the typical appearances of a toxic drug reaction with a mixed infiltration of cells. Occasional patients reported pruritus without accompanying rash. In most cases, the rash was mild, easily manageable with antihistamines and/or topical steroids, and gradually subsided without interrupting therapy. However, a troublesome skin rash was the most frequent reason (in <1% of patients overall) for the permanent discontinuation of therapy. Approximately 3% of patients developed severe skin rashes, some with an exfoliative component. Re-challenge was usually but not always positive.

## GIST

Treatment with Imatinib Mesylate was generally well tolerated, although nearly every patient experienced at least some minor adverse events. The most frequently reported adverse events were edema, nausea, diarrhea, musculoskeletal pain, fatigue, rash, headache, and abdominal pain. Most events were of mild to moderate severity. Superficial edema, most frequently periorbital or lower limb edema, was managed with diuretics, other supportive measures, or by reducing the dose of Imatinib Mesylate. Severe (CTC grade 3/4) superficial edema was observed in 2 patients including face edema in one patient. No major differences were seen in the severity of adverse events between the 400mg or 600mg treatment groups, although overall incidence of adverse events was somewhat higher in the 600mg treatment group. Adverse events with a suspected relationship to therapy occurring in greater than 10 % of patients in any group are presented in Table 5.

**Table 5** Adverse events with suspected relationship to therapy in GIST  
(≥ 10% in any group)

Preferred terms	All grades			Grade 3 / 4		
	400 mg n = 73	600 mg n = 74	All doses N = 147	400 mg n = 73	600 mg n = 74	All doses N = 147
Any AE	97	99	98	21	22	21
Edema/fluid retention	71	77	74	1	1	1
Periorbital edema	45	50	48	0	0	0
Edema lower limb	26	15	20	0	0	0
Face edema	8	12	10	1	0	1
Edema	7	14	10	0	0	0
Eyelid edema	7	8	8	0	0	0
Nausea	51	54	52	1	1	1
Diarrhea	40	50	45	1	3	2
Myalgia / musculoskeletal pain	37	42	40	0	0	0
Fatigue	30	39	35	0	0	0
Dermatitis / rash	25	37	31	3	3	3
Headache	19	32	26	0	0	0
Abdominal pain	26	26	26	1	0	1
Flatulence	19	24	22	0	0	0
Vomiting	14	12	13	0	1	1
Any hemorrhage	11	14	12	4	5	5
Tumor hemorrhage	1	4	3	1	4	3
Upper GI bleed / perforation	4	3	3	4	1	3
Dyspepsia	10	12	11	0	0	0
Lacrimation increased	7	12	10	0	0	0
Anemia	6	12	9	1	3	2
Loose stools	7	10	8	0	0	0
Taste disturbance	3	14	8	0	0	0

There was no hyperuricemia or evidence of tumor lysis syndrome, even in patients with very rapid

decreases in tumor volume. The most medically significant adverse events were gastrointestinal or intra-abdominal hemorrhage in patients with large bulky tumors, which occurred in approximately 5 % of patients.

## **6.2 Dose Modifications for Non-Hematological Toxicity**

### **Grade 2**

If the patient experiences a Grade 2 non-hematologic toxicity, study drug must be withheld until the toxicity has resolved to  $\leq$  Grade 1. Imatinib Mesylate may then be resumed at the same daily dose. If the Grade 2 toxicity recurs, Imatinib Mesylate must be withheld until the toxicity has resolved to  $\leq$  Grade 1, and the daily dose must be reduced to 400 mg for patients receiving 600mg of Imatinib Mesylate or to 600mg for patients receiving 800mg of Imatinib Mesylate.

### **Grade 3/4**

If the patient experiences Grade 3/4 toxicity study drug must be withheld until the toxicity has resolved to  $\leq$  Grade 1 and the daily dose must be reduced to 400mg for patients receiving initially 600mg of Imatinib Mesylate or to 600 mg for patients receiving 800 mg. If the Grade 3/4 toxicity recurs, Imatinib Mesylate must be withheld until the toxicity has resolved to  $\leq$  Grade 1, and the daily dose must be reduced to 300mg once daily for patients receiving 400mg of Imatinib Mesylate or to 400mg daily for patients receiving 600mg of Imatinib Mesylate.

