## **5.0 Treatment Plan**

### **5.1 Phase I Part**

The first 3 patients will be started at a dose of 300 mg Imatinib Mesylate twice a day and the dose will be escalated to 400 mg twice a day after 2 weeks in the same patient if no toxicity occurs. If grade 3/4 toxicity is observed, the dose of Imatinib Mesylate will be reduced as outlined in section 6.2 and 6.3 and the subsequent patients will be treated at that dose levels. The dose for Letrozole will be 2.5 mg, per oral, given once a day.

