### **5.2 Phase II Part**

The dose for Imatinib Mesylate will 400 mg, twice a day (total daily dose 800 mg), per oral. Imatinib Mesylate is a local irritant and must be taken in a sitting position with a large (250 mL) glass of water. (Direction of use on medication label: Take as directed with a large glass of water). Imatinib Mesylate should not be taken with grapefruit juice.

The dose for Letrozole will be 2.5 mg, once a day, per oral.

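### The first-event Grade 3/4 rule in section 6.2 does not say which dose decides the reduction, and leaves some reachable patients with two targets or none

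*Combined protocol and SAP*

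**What the plan says.** - **Run-in (section 5.1).** "The first 3 patients will be started at a dose of 300 mg Imatinib Mesylate twice a day". Two weeks later, provided there has been no toxicity, each of them moves up to the 400 mg twice-daily dose. A Grade 3/4 toxicity leads instead to a reduction under 6.2 and 6.3. For those enrolled later, the section adds that "the subsequent patients will be treated at that dose levels".
- **Phase II (section 5.2).** The dose is "400 mg, twice a day (total daily dose 800 mg), per oral".
- **Section 6.2, recurrent Grade 2.** After the drug is withheld, the dose is "reduced to 400 mg for patients receiving 600mg of Imatinib Mesylate or to 600mg for patients receiving 800mg of Imatinib Mesylate".
- **Section 6.2, first Grade 3/4 event.** After the drug is withheld, a reduction is mandatory: "reduced to 400mg for patients receiving initially 600mg of Imatinib Mesylate or to 600 mg for patients receiving 800 mg".
- **Section 6.2, recurrent Grade 3/4.** The dose becomes "300mg once daily for patients receiving 400mg of Imatinib Mesylate or to 400mg daily for patients receiving 600mg of Imatinib Mesylate".
- **Section 6.3, hematological Grade 3/4 that recurs or lasts beyond two weeks.** Treatment restarts at 300 mg from 400 mg, and at 400 mg from either 600 or 800 mg.

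The word *initially* occurs in only one of these rules, and in only one of that rule's two branches.

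**The concern.** A mandatory rule should give one result for every patient who can reach it. Here the first branch appears to look at where the patient started, and the second at what she receives now. The trial's own run-in produces patients for whom these differ, because the same patient starts at one dose and is then raised to another.

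The result also does not stay with that patient. Section 5.1 turns the reduced dose of a run-in patient into the dose for those who follow. If the site cannot tell which branch applies, the regimen whose objective response rate section 13.0 sets out to estimate could depend on how one word was read. Section 6.4 itself allows that a clinically relevant dose-response may matter. Separately, a patient for whom no branch applies must have her dose reduced, yet the protocol gives no dose at which to resume.

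**Working it through.** **Daily doses.** Phase II: 2 × 400 = 800 mg/day, which matches the total printed in section 5.2. Run-in start: 2 × 300 = 600 mg/day (product not printed). After escalation the same patient receives 800 mg/day.

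**Applying the first-event sentence.** Each reachable combination of starting and current dose is taken through the sentence on three readings: as worded with *initially* meaning starting dose (first branch by starting dose, second by current dose); both branches by current dose; both by starting dose. Entries are targets in mg/day.

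| Patient at first Grade 3/4 non-hematologic event | Start | Now | As worded | Both by current dose | Both by starting dose |
|---|---|---|---|---|---|
| Run-in, before escalation | 600 | 600 | 400 | 400 | 400 |
| Run-in, escalated | 600 | 800 | **400 and 600** | 600 | 400 |
| Run-in, escalated, back to 600 for recurrent Grade 2 | 600 | 600 | 400 | 400 | 400 |
| Started at 800, unchanged | 800 | 800 | 600 | 600 | 600 |
| Started at 800, reduced to 600 for recurrent Grade 2 | 800 | 600 | **none** | 400 | 600 (no reduction) |
| Started at 800, now at 400 (via 6.3, or the Grade 2 rule applied twice) | 800 | 400 | **none** | **none** | 600 (above current dose) |
| Started at 600, reduced to 400 for recurrent Grade 2 | 600 | 400 | 400 (no reduction) | **none** | 400 (no reduction) |

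**Recurrent events.** A patient reduced from 800 to 600 for Grade 3/4 toxicity, in whom that toxicity recurs, is covered by the next sentence of 6.2: 600 goes to 400. She is not in a gap.

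**Hematological events.** Section 6.3 has no mixed wording. It takes 800 to 400, so it does not lead to the 600 mg state in the fifth row, but it does lead to the 400 mg state in the sixth.

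**Possible spread from the run-in.** Counting the first 3 patients within the 45 of sections 3.1 and 13.0, 45 − 3 = 42 patients follow, and 42/45 = 93%. The two competing targets are 400/800 = 50% and 600/800 = 75% of the planned daily dose. For the double target to reach later patients, a run-in patient must be escalated (section 5.1 requires no toxicity first) and must then have a first Grade 3/4 non-hematologic event while on 800 mg. The documents give no probability for this sequence.

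**The case against.** The strongest reply is that *initially* need not mean the starting dose. The sentence deals with the first Grade 3/4 event and the next one with recurrence, so the word can mean the dose at that first event. Every parallel rule is worded by the dose being received. On this reading 800 goes to 600 and 600 goes to 400, and the recurrence sentence picks up from exactly those two results. The double target and the gap at 600 mg both disappear, as the table shows. This reading is reasonable, so a proven contradiction cannot be claimed.

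It does not settle the matter. The protocol does not say that this is the meaning, and the word then adds nothing, in one branch only. As planned, the only patients who start at 600 mg/day are those in the run-in, which makes the starting-dose reading natural too. And the milder reading still gives no target for a patient already at 400 mg.

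A reader might infer three stronger claims, none of which the documents support:

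- **That any patient reduced from 800 to 600 mg falls outside both branches.** Recurrence after a Grade 3/4 reduction is covered by the next sentence. A run-in patient brought back to 600 still meets the first branch. The clear case, on the starting-dose reading, is the one that began at 800 and came down for recurrent Grade 2 toxicity. Whether a different Grade 3/4 toxicity after an earlier Grade 3/4 reduction counts as a recurrence is arguable.
- **That 42 of 45 patients are affected.** This is a ceiling, conditional on the run-in event described above. Without toxicity in the run-in, section 3.0 has later patients start at 800 mg/day.
- **That the statistical design is in error.** No sample size, stopping boundary or operating characteristic in section 13.0 depends on this wording.

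**Conclusion.** The first-event Grade 3/4 rule in 6.2 is ambiguous and leaves reachable cases unassigned.

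- **If *initially* means starting dose:** up to 3 run-in patients, while on 800 mg/day, have two targets (400 and 600 mg/day), and section 5.1 could carry the choice to at most 42 later patients. A patient who started at 800, was reduced to 600 for recurrent Grade 2 toxicity and then has a first Grade 3/4 event has no target.
- **If it means the dose at the first event:** both of those problems vanish. A patient already at 400 mg, by way of the Grade 2 rule or section 6.3, still faces a mandatory reduction with no stated target.

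None of the three readings gives every reachable patient exactly one reduced dose, so clarification is needed whichever meaning was intended. The counts assume that the run-in patients belong to the 45 and that escalation proceeds as section 5.1 describes. No printed statistical figure is wrong.

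**What to change.** The sponsor and investigator should state what *initially* refers to, and reconcile sections 5.1, 6.2 and 6.3 on one stated basis. Each daily dose that the trial can reach should have exactly one action at a first and one at a recurrent Grade 3/4 event, including a first non-hematologic event in a patient whose dose was already reduced for another reason. Section 5.1 should refer to that statement, so that a run-in event yields a single dose for subsequent patients.

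Defining the word alone would resolve the double target only if the definition leads to a single branch, and it would not close the gap at 400 mg; a short table would do both. Which basis and which doses to use is for the sponsor and investigator, and none is proposed here.

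The cost is one line or one table in a protocol amendment, with no added patients, visits or procedures and no change to section 13.0.

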## **6.3 Dose modifications for hematological toxicity**

### **Grade 2**

No dose interruptions or reductions will be performed for Grade 1/2 hematological toxicity.

### **Grade 3/4**

If patient experiences a Grade 3/4 hematological toxicity, defined as an ANC  $< 1 \times 10^9/L$ , or a platelet count  $< 50 \times 10^9/L$ , Imatinib Mesylate must be withheld until the toxicity has resolved to  $\leq$  Grade 2. ANC will takes precedence over a WBC count in determining the degree of neutropenia (doses should not be interrupted for a patient with a WBC  $< 2.0 \times 10^9/L$  but ANC  $> 1 \times 10^9/L$ ). If the toxicity resolves within two weeks, Imatinib Mesylate treatment may be resumed at the same dose. If the Grade 3/4 toxicity recurs or persists for longer than two weeks, Imatinib Mesylate must be withheld and then recommenced at the dose of 300mg once daily for patients receiving 400mg of Imatinib Mesylate or 400 mg for patients receiving 600 mg of Imatinib Mesylate or 800mg of Imatinib Mesylate, once toxicity has resolved to  $\leq$  Grade 2.

No dose reductions will be performed for grade 3/4 anemia. If the patient develops anemia, s/he may be transfused at the discretion of the investigator.

## **6.4 Dose Modifications for Other Reasons**

The optimal dose of Imatinib Mesylate in an as-yet undefined spectrum of diseases is unknown, however, the possibility of a clinically relevant dose-response may be of importance. Therefore, it is possible that higher doses of Imatinib Mesylate might induce responses even if a lower dose fails. If vomiting occurs, no additional trial medication should be taken that day in an effort to replace the material that has been vomited.

## **6.5 Concomitant Therapy**

In general, concomitant medications and therapies deemed necessary for the supportive care and safety of the patient, such as bisphosphonates, are allowed, provided their use is documented in the patient records and on the appropriate case report form. The administration of any other therapies intended to treat the primary condition including chemotherapy and biologic agents is not, however, permitted. Similarly, the use of other concurrent investigational drugs is not allowed.

Because of the inherent risk of either reduced activity or enhanced toxicity of the concomitant medication and/or Imatinib Mesylate, drugs known to interact with the same CYP450 isoenzymes (2D6 and 3A4) as Imatinib Mesylate should be used with caution. Patients using concomitant medications known to be metabolized by these cytochrome p450 enzymes will not be excluded from the study. (See Appendix D) However, the patients must be carefully monitored for potentiation of toxicity due to individual concomitant medication. Special care has to be given to the concomitant use of acetaminophen (e.g. Tylenol or Percocet, paracetamol Panadol, etc.) with Imatinib Mesylate. Any use of concomitant medication must be captured in the concomitant medication CRF.

Since warfarin is metabolized through the CYP450 system, no therapeutic anticoagulation with warfarin (e.g. Coumadin® or Coumadine®) will be permitted in patients participating in this study. As an alternative, therapeutic anticoagulation may be accomplished using low-molecular weight heparin (e.g. Lovenox) or heparin. A mini-Dose coumarin derivative (equivalent to 1 mg QD Coumadin®) is permitted for prophylaxis of central venous catheter thrombosis, at the discretion of the treating physician. In general, the use of Coumadin® is discouraged on this protocol.

The routine use of systemic corticosteroid therapy is not permitted. Prophylactic anti-emetics should be withheld until the patient has experienced grade 1 nausea or vomiting.

Prophylactic use of loperamide (e.g. Imodium® , with suggested dosing as start: 4mg p.o. x 1, than 2mg p.o. after each loose stool, max 16mg/d) is recommended for patients experiencing grade 1 or 2 diarrhea, before dose interruption.

## **6.6 Treatment Compliance**

Records of study medication used, dosages administered, and intervals between visits will be kept during the study. Drug accountability will be noted and at the completion of the trial. Patients will be asked to return all unused medication at the end of the study.

